3. ABBREVIATIONS AND DEFINITIONS

3.1. Abbreviations

ADR	Adverse drug reaction
AE	Adverse event
CIOMS	Council for International Organization of Medical Science
CRF	Case Report Form
CRO	Contract Research Organization
CTA	Clinical Trial Application
DSMB	Data and Safety Monitoring Board
DSUR	Development Safety Update Report
EC	Ethics Committee
GCP	Good Clinical Practice
IB	Investigators Brochure
ICF	Informed Consent Form
ICH	International Conference on Harmonization
IMP	Investigational Medicinal Product
LVSL	Last Visit of Last Subject
MedDRA	Medical Dictionary for Regulatory Activities
NIMP	Non-Investigational Medicinal Product
PeIMP	Products equivalent to the IMP
PI	Principal Investigator
QP	Qualified Person
ReTNIMP	Regardless to Trial NIMP
SAE	Serious Adverse Event
SAR	Serious Adverse Reaction
SDR	Serious Drug Reaction
SmPC	Summary of Product Characteristics
SOP	Standard Operating Procedure
SUSAR	Suspected Unexpected Serious Adverse Reactions
csPCa	clinically significant prostate cancer
PSA	prostate specific antigen
EAU	European Association of Urology

mpMRI	multiparametric magnetic resonance imaging
PSMA	prostate specific membrane antigen
PET	positron emission tomography
ROI	region of interest
OSR	Ospedale San Raffaele
ROC	Receiver operating characteristics

3.2. Definitions

Not applicable.

4. BACKGROUND AND RATIONALE

Prostate cancer (PCa) is the second most common cancer in men, with 1,414,259 new cases in 2020, accounting for 15.1% of all cancer diagnoses within the male population (1). The current EAU Guidelines for PCa recommend performing mpMRI before prostate biopsy in men with clinical suspicion of PCa (2). However, the accuracy of mpMRI in detecting csPCa remains suboptimal and a significant proportion of unnecessary biopsies are performed in men with suspicious lesions on mpMRI (3). Several efforts were made to identify new diagnostic strategies to implement mpMRI performances. The use of PSMA PET, widely implemented for clinical management of PCa both in recurrent and primary setting, has recently gained interest for diagnostic purposes. In 296 men with suspicion of PCa, the combined use of ⁶⁸Ga-PSMA PET and mpMRI for PCa diagnosis showed improved sensitivity and negative predicted value for csPCa (4). Based on these results, the combination of mpMRI and ⁶⁸Ga-PSMA PET might reduce the number of prostate biopsies required to diagnose csPCa. In this prior study, mpMRI and ⁶⁸Ga-PSMA PET have been acquired and interpreted separately, with the risk of introducing potential confounders. Moreover, imaging-guided targeted biopsies were not systematically performed.

In this project, the role of hybrid PET/MRI with ¹⁸F-PSMA will be evaluated in PCa diagnosis. The major advantages of this innovative technology are the simultaneous acquisition of PET and mpMR imaging by using a fully hybrid PET/MRI scan and the use of ¹⁸F-PSMA with improved spatial resolution compared to ⁶⁸Ga-PSMA, due to its lower positron energy.

5. RISK/BENEFIT ASSESSMENT

5.1. Known Potential Risks

A potential risk of this study is patients' compliance regarding the execution of a PET exam in addition to the standard of care MRI and the prolonged scan time. The scan will be performed simultaneously on a dedicated hybrid PET/MRI whole body scanner and additional data regarding potential disease extension will be collected concomitantly. Longer execution time, though, will offer added value for describing disease both to the patient as well as for the scope of this study. The side effects of contrast medium for MRI are very low (standard of care), as are those documented by internal unpublished data on the use of ¹⁸F-PSMA. Our goal is also to optimize these dedicated PET/MRI acquisition protocols in terms of duration, hopefully increasing patient compliance. The interventions proposed in this trial are aligned with what suggested by the EAU Guidelines for prostate cancer diagnosis. Specifically, all patients will undergo mpMRI as recommended by EAU guidelines. In addition to mpMRI, all patients will undergo a concomitant ¹⁸F-PSMA PET whose results will be evaluated jointly with those of the mpMRI during the same diagnostic session. Therefore, participants will be offered the diagnostic gold standard plus additional ¹⁸F-PSMA PET, whose use in the diagnostic pathway has been already proposed (4,5). Regarding the toxicity and radioactive exposure associated with the use of radionuclides PSMA, several studies have demonstrated the low exposure to radiation and showed no adverse effects or toxicity (6). All patients will then undergo a 12-core SBx as also recommended by the EAU guidelines plus TBx in case of either ¹⁸F-PSMA PET or mpMRI would show suspicious lesion/s, adverse events (AE) will be recorded by a member of the research team or clinical team on an AE report form. All serious AE (SAE) will be recorded on a SAE report form. Both AE and SAE should be recorded in the medical notes.

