2. SYNOPSIS

Trial Title	Fully hybrid 18F-PSMA PET/MRI as one-stop approach for the diagnosis of clinically significant prostate cancer	
Protocol Acronym/Number	RF-2021-12372278	
Protocol Version and Date	v2.0, 30 GEN 2023	
EudraCT number	NA	
Sponsor	IRCCS Ospedale San Raffaele [name]	
Funding Source(s)	Italian Ministry of Health	
Principal Investigator	[name], U.O. of Nuclear Medicine	
Trial Description	
This project aims to evaluate the role of fully hybrid PET/MRI with 18F-PSMA and multiparametric MR imaging (mpMRI) as one-stop approach for the diagnosis of clinically significant prostate cancer (csPCa).
 
Our main hypothesis is that adding 18F-PSMA PET to mpMRI prior to biopsy, will reduce the number of false negative findings, while at the same time, allowing also to reduce the number of unnecessary prostate biopsies in patients with low-risk, clinically indolent PCa.
	
	Primary	Secondary
Objectives	To assess the accuracy and the predictive value of fully hybrid 18F-PSMA PET/MRI for the diagnosis of csPCa	
 1) To compare the proportion of csPCa missed by 18F-PSMA PET scan or mpMRI alone 2) To report the reduction in the detection of clinically insignificant PCa when combining mpMRI and 18F-PSMA PET, and consequently the proportion of unnecessary biopsies potentially spared.
Endpoints	Diagnostic accuracy measured with sensitivity, specificity, positive and negative predicted value	
 1) The number of csPCa missed by PET and MR imaging when read independently 2) Only in patients with positive mpMRI and negative 18F-PSMA PET: The proportion of clinically insignificant PCa
Time point(s)	day 0: 18F-PSMA PET/MRI day 90 (+/- 90): prostate biopsy	
Phase	Phase II	
Trial Design	Monocentric, single-arm, prospective	

Trial Population	Men with clinical suspicion of csPCa.
Inclusion Criteria	1) Men at least 18 years of age referred with clinical suspicion of prostate cancer candidate for prostate biopsy 2) Feasibility to undergo all procedures listed in protocol 3) Ability to provide written informed consent
Exclusion Criteria	1) Prior diagnosis of prostate cancer 2) Contraindication to MRI (e.g. claustrophobia, pacemaker, estimated GFR lower or equal to 50mls/min) 3) Contraindication to prostate biopsy
Intervention(s)	
IMP(s)	18F-PSMA, 4 MBq/Kg, intravenous administration
NIMP(s)	Not applicable.

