8. TRIAL DESIGN

In this single-arm phase II, prospective, monocentric study we will test whether addition of 18F-PSMA PET scan to mpMRI helps improving the diagnostic pathway efficiency in identifying those men who should necessarily undergo TBx, because of high-risk to harbor csPCa.

Furthermore, the combined use of 18F-PSMA PET and mpMRI for the diagnosis of PCa may also result in a reduced number of follow-up procedures in those patients who can safely avoid a prostate biopsy given the very low risk of harboring csPCa using a single, one-stop approach with both imaging modalities. A more efficient pre-biopsy triage test using the fully hybrid 18F-PSMA PET/MRI might result in the reduction of the total number of biopsies for men with a clinical suspicion of PCa, reducing also patient discomfort combining two different diagnostic procedures in one single step and avoiding, whenever possible, the biopsy-related side effects.

A total of 167 consecutive patients with a clinical suspicion of csPCa (defined as the presence of PCa with ISUP grade equal or higher to 2), referred to simultaneous 18F-PSMA PET/MRI with mpMRI, will be identified and enrolled. PET/MRI images will be qualitatively and quantitatively evaluated by an experienced Nuclear Medicine and an experienced Radiologist physicians. In particular, for qualitative evaluation, lesions classified as PI-RADS higher or equal to 3 on mpMRI images and/or showing pathologically increased 18F-PSMA uptake on PET images, will be considered as positive for csPCa. All men will then receive a prostate biopsy (12-core random systematic prostate biopsy plus eventual targeted biopsy) as back-up histology according to the results of PET/MR imaging.

Specifically, patients with both positive mpMRI and 18F-PSMA PET, defined as the presence of one or more lesions with PI-RADS higher or equal to 3 and an increased uptake of 18F-PSMA, will receive a 12-core random systematic prostate biopsy (TRUS-Bx) in addition to MRI targeted biopsy (MRI-TBx) and 18F-PSMA PET targeted biopsy (PSMA PETTBx).

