MpMRI is the standard of care diagnostic tool for staging and restaging in patients with Pca. The high expertise of the Center in prostate MRI has shown negligible inter-reader variability. All MRIs will be analysed by an experienced Radiologist (6 years of experience in prostate mpMRI). All PET exams will be analysed by an expert Nuclear Medicine physician (>10 years of experience in prostate PET). Furthermore, to avoid bias in the qualitative image analysis, PET and mpMR scans will be evaluated blind to the results of the other imaging modality. For efficacy analyses that require complete patient data, missing values during the treatment period will be replaced, for all variables, with the LOCF technique (Last Observation Carried Forward). Imputed values will be included in the analysis set(s), but will not change the original clinical database. For subjects who interrupt prematurely the trial due to the "adverse event", the BOCF technique (Basal Observation Carried Forward) will be used instead of the LOCF, in order to avoid the allocation of a positive result to patients to be considered treatment failures.

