10.6. Preparation, Administration and Accountability of the Trial Treatments

Radiotracer synthesis: 18F-PSMA synthesis is performed using an automatic synthesis module (NEPTIS) through the incorporation of 18F (produced by the IBA 18 MeV cyclotron) in a PSMA 1007 precursor molecule; after formulation and sterilization on a 0.22 µm filter membrane, quality control is performed to evaluate the chemical, radiochemical, radionuclidic and microbiological purity of the final product in compliance with the monograph of Eu. Ph. 3116.

PET/MR acquisition protocol: PET/MRI will start approximately 90 minutes after intravenous administration of 4 MBq/Kg of 18F-PSMA. A PET/MR total body acquisition and a high statistics pelvic PET simultaneously acquired to mpMRI will be performed. Using 3 Tesla PET/MR system the endorectal coil is not needed for the MR acquisition thus increasing patient compliance.

MpMRI protocol will follow ESUR guidelines: axial T2 weighted sequence with large field of view (FOV), axial and sagittal T2 weighted sequence with small FOV, DWI sequence with small FOV $b = 50, 800, 1400; 2000 \text{ s/mm}^2$ and ADC maps, T1-Lava Flex sequence of the pelvic region pre-contrast and post-contrast, a high temporal resolution T1 perfusion sequence after IV injection of 0.1 mmol/kg bolus of gadobutrol at a flow rate of 3.5 mL/s.

PET/MRI qualitative analysis: images will be evaluated by expert Nuclear Medicine and Radiologist physicians blinded to each other on the Advantage Workstation (AW, General Electric Healthcare, Waukesha, WI, USA) where PET, MRI and fused PET/MRI images can be visualized in axial, coronal and sagittal planes. Focal uptake of 18F-PSMA higher than background and not associated with physiologic uptake was considered positive. For mpMRI, T2W morphological, diffusion (DWI) and perfusion (DCE) sequences will be used to define lesions according to PIRADS v. 2.1 classification (7). Lesions classified as PI-RADS ≥ 3 on mpMRI images and/or showing increased 18F-PSMA uptake on PET, will be considered positive for csPCa.

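### The plan has PET and mpMRI evaluated jointly in one section and read blind in others, with no rule on image access, read order or locking, so the single-modality comparisons are unprotected

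*Combined protocol and SAP*

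**What the plan says.** All references are to the combined protocol and SAP. It describes how the images are read in four places.

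- Section 5.1 (Known Potential Risks) says that all patients have a concomitant PET "whose results will be evaluated jointly with those of the mpMRI during the same diagnostic session".
- Section 8 (Trial Design), among the measures against bias, says that "PET and mpMR scans will be evaluated blind to the results of the other imaging modality". It assigns mpMRI to a radiologist and PET to a nuclear medicine physician.
- Section 10.6, under qualitative analysis, says that "images will be evaluated by expert Nuclear Medicine and Radiologist physicians blinded to each other on the Advantage Workstation", and continues: "where PET, MRI and fused PET/MRI images can be visualized in axial, coronal and sagittal planes".
- The Synopsis gives the first secondary endpoint as "The number of csPCa missed by PET and MR imaging when read independently".

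The combined call is defined twice. In Section 10.6, lesions with PI-RADS 3 or higher "and/or showing increased 18F-PSMA uptake on PET, will be considered positive for csPCa". Section 8 has the same rule: "and/or showing pathologically increased 18F-PSMA uptake on PET images, will be considered as positive for csPCa". Section 8 then compares PET/MRI findings with biopsy histology to obtain the accuracy measures.

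The primary objective in Section 6 concerns the hybrid examination. The primary endpoint there, and Section 16.1, refer to the accuracies of PET and mpMRI and do not mention the combined call. Section 16.1 assigns the McNemar test to the csPCa missed by either modality alone. Section 8 restricts the spared-biopsy analysis to men with positive mpMRI and negative PET.

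**The concern.** Two analyses need calls that were truly made on one modality: the McNemar comparison and the mpMRI-positive/PET-negative subset. If a reader has seen the other scan, a miss can turn into a detection, or a doubtful finding can be upgraded or dropped. The recorded result is then no longer the performance of that modality alone.

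The text does not rule this out. Joint evaluation in one session and mutually blind reading cannot both describe the same act, and no section puts them in sequence. Blinding two people to each other is also weaker than blinding each to the other's images: a nuclear medicine physician who never speaks to the radiologist can still open the T2 or fused series. Section 10.6 plans cross-modality viewing for other purposes. PET targets are contoured on PET co-registered with mpMRI, and volumes for radiomics are segmented on PET, T2-weighted images and ADC maps by both specialties. Without a lock, a call could be revised after those steps. An unblinded read cannot be undone at analysis.

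**Working it through.** **1. The plan's own figure.** Inputs from Section 16.2: sensitivity 96%, precision 4 points, 95% confidence, prevalence 56%.

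- csPCa cases needed: 1.96² × 0.96 × 0.04 / 0.04² = 92.2, rounded up to 93.
- Patients: 93 / 0.56 = 166.07, rounded up to 167. The figure reproduces.
- Expected csPCa among 167 patients: 167 × 0.56 = 93.5. The half-width at 96% is then 1.96 × √(0.96 × 0.04 / 93.5) = 3.97 points.

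Nothing in this point alters 167.

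**2. What the reading instructions settle.**

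| Question | Answer in the plan |
|---|---|
| Who reads which modality? | Stated (Section 8) |
| Are readers blind to the other modality's results? | Yes in Section 8; Section 5.1 describes joint evaluation |
| Are readers blind to the other modality's images? | Not stated; the workstation can show all of them (Section 10.6) |
| Order of reads, contouring, segmentation and joint evaluation? | Not stated |
| When does a single-modality call become final? | Not stated |

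**3. Effect on the McNemar test, fixed counts.** The documents give no discordant counts, so these are assumed. With b and c the csPCa missed by one modality only, the exact two-sided p is 2 × Σ C(b+c, k) / 2^(b+c), for k from 0 to the smaller of b and c.

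- 14 v 4 (no leakage): 2 × 4048 / 262144 = 0.031.
- 10 v 4 (four of the 14 misses corrected by sight of the other scan): 2 × 1471 / 16384 = 0.180.
- 14 v 2 (two of the 4 misses corrected instead): 2 × 137 / 65536 = 0.004.

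The direction depends on which reader is influenced.

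**4. Effect on power when both readers are influenced equally.** Assumed: 94 csPCa cases; 14% missed by mpMRI only, 4% by PET only, 4% by both. Leakage corrects the same fraction of the single-modality misses on each side. Power is for the exact McNemar test at 0.05, from 20,000 simulated trials per row.

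| Misses corrected | mpMRI sensitivity | PET sensitivity | Difference (points) | Power | And/or sensitivity |
|---|---|---|---|---|---|
| 0% | 82% | 92% | 10 | 56% | 96% |
| 25% | 85.5% | 93% | 7.5 | 42% | 96% |
| 50% | 89% | 94% | 5 | 23% | 96% |

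**5. The and/or composite.** It stays at 100% − 4% = 96% because every corrected case was already positive on the other modality. This covers upgrades only. If a reader withdraws a doubtful call because the other scan looks clean, and the other read is negative, the composite changes too.

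**6. The spared-biopsy subset.** In the same scenario the csPCa in the mpMRI-positive/PET-negative group are those missed by PET only: 0.04 × 94 = 3.8 men without leakage, 2.8 at 25% and 1.9 at 50%. Men without csPCa also leave if the PET reader upgrades faint uptake at an mpMRI lesion. The proportion of insignificant cancers in the subset can therefore move either way.

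**The case against.** The strongest reply is that the operative text agrees with itself. Section 5.1 is a risk and benefit paragraph. It speaks of results being evaluated jointly, which can mean that two finished reads are put together. Sections 8 and 10.6 and the Synopsis all call for blind or independent reading, and Section 8 gives the modalities to different specialists. The workstation sentence describes what the software can display, not what each reader opens. Co-registered images are needed for targeting in any case.

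Much of this stands. A reader might infer that contaminated reading is planned; the documents do not support that. It is a risk left open. What the reply does not supply is the missing instruction: no section says that joint evaluation follows completed reads, restricts image access or locks a call.

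A reader might also see Section 4 as self-contradictory, because it faults an earlier study in which the scans "have been acquired and interpreted separately, with the risk of introducing potential confounders". That passage criticises separate acquisition and interpretation together. The advantages it then claims for this trial are simultaneous acquisition and the tracer. It does not promise a joint read.

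Finally, the counts above are assumed, and leakage on one side alone can be chosen to push p either way. That is correct: they show sensitivity to leakage, not an expected effect.

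**Conclusion.** The point holds as a gap in the reading procedure. The sections conflict, and as written a single-modality call can be informed by the other modality. The exposure is confined mainly to the secondary McNemar comparison and the mpMRI-positive/PET-negative subset. Bias can go in either direction, and its size cannot be derived from the documents. In the symmetric scenario, which rests on assumed miss rates, power falls from about 56% to 42% or 23%. The and/or sensitivity is unchanged there, and may be little affected in practice.

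A reader might go further and infer that no hybrid result is recorded or would ever be scored. The documents do not support that: Sections 8 and 10.6 define the and/or call, and Section 8 compares PET/MRI findings with histology. The narrower gap is that Sections 6 and 16.1 do not say this composite is the result analysed for the primary objective. The absence of a separate consensus read is a design choice, not an error.

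This should be settled before reads are made, since it cannot be repaired afterwards.

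**What to change.** Reconcile Sections 5.1, 8 and 10.6 into one ordered procedure.

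1. The nuclear medicine physician records the PET result with the diagnostic mpMRI sequences and the fused display hidden.
2. The radiologist records PI-RADS with PET hidden.
3. Both results are locked in the CRF before any joint evaluation, biopsy-target contouring or volume segmentation.
4. The locked reads supply the missed-csPCa endpoint, the mpMRI-positive/PET-negative subset and the and/or composite.
5. Section 16.1 states that the and/or composite is the PET/MRI result for the primary objective, and Section 6 is aligned with it.

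A separate joint read can be added as optional and exploratory; it is not needed to close the gap. The cost is protocol wording, a CRF lock and slightly more reading logistics for the two readers already planned. No additional patients or readers are required.

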5.2. Known Potential Benefits

In this study we will implement and assess a novel ^{18}F -PSMA PET targeted software-assisted fusion biopsy method to accurately target ^{18}F -PSMA PET ROIs and to provide reliable data on ^{18}F -PSMA PET diagnostic accuracy. We will develop an efficient and time-effective one-stop session ^{18}F -PSMA PET/mpMRI examination for PCa diagnosis by using a fully hybrid PET/MRI. The simultaneous acquisition of PET using a new radiotracer such as ^{18}F -PSMA and mpMRI provides metabolic structural and functional information regarding PCa status in a whole-body single session examination, thus representing an improvement and innovation for PCa staging. Data provided by this study will have potential clinical implications such as the improvement of csPCa detection and the reduction of clinically indolent PCa diagnosis, thus overdiagnosis and overtreatment.

5.3. Assessment of Risks and Benefits ratio

The prolonged acquisition time that characterizes fully hybrid PET/MRI is necessary to provide a one-stop-shop for the diagnosis of csPCa. Furthermore, PSMA PET, despite obviously entailing a low radiation exposure to patients, is a safe procedure already recommended for the characterization of PCa both in the staging and restaging phase by international guidelines (2). The low risk that this protocol entail is therefore justified by its potential clinical implications such as the improvement of csPCa detection and the reduction of clinically indolent PCa diagnosis, thus overdiagnosis and overtreatment.

6. OBJECTIVES AND ENDPOINTS

Objectives	Endpoints	Time point(s)
Primary Objective To assess the accuracy and the predictive value of fully hybrid ^{18}F -PSMA PET/MRI for the diagnosis of csPCa	Primary Endpoint Diagnostic accuracies of ^{18}F -PSMA PET and mpMRI will be calculated by means of sensitivity: true positive/(true positive + false negative) and specificity: true negative/(false positive + true negative) using the prostate biopsy result as reference standard.	PET/MRI examination at day 0, and biopsy at day 1-30 (within a month from imaging study)
Secondary Objectives To compare the proportion of csPCa missed by ^{18}F -PSMA PET scan or mpMRI alone	Secondary Endpoints The proportion of csPCa (defined by analysis of prostate biopsy cores, ISUP grade equal or higher than 2) missed by PSMA PET scan or mpMRI alone will be calculated.	PET/MRI examination at day 0, and biopsy at day 1-30 (within a month from imaging study)
Exploratory Objectives To assess the proportion of unnecessary biopsies potentially spared	Other Number of clinically insignificant PCa (ISUP grade 1) identified combining mpMRI and ^{18}F -PSMA PET.	PET/MRI examination at day 0, and biopsy at day 90 (+/-90)

